5.1. General Statistical Considerations

All statistical analyses will be performed using SAS® version 9.0 or higher. The specific analyses to address the objectives will be described in the Statistical Analysis Plan.

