5.4.1.2. Assessing the Precision of Flortaucipir F 18 PET Scan Reads

The second primary objective will assess inter-reader reliability.

Primary Objective Analysis 2

The inter-reader reliability of flortaucipir F 18 PET scan visual interpretation will be assessed using kappa statistics. Fleiss' Kappa and the associated 95% CI will be calculated based on 5 readers' visual interpretations on the 242 scans (comprised of 83 scans from Study A16 autopsy cases, and 159 cases from Study A05). The p-value will be calculated using normal approximation method. The lower bound of the 95% CI for Fleiss' Kappa must be greater than or equal to 0.6 to meet the inter-reader reliability criterion. If the scan is selected (by random) to be read twice for the intra-reader reliability assessment, the first read will be used for the second primary objective analysis; for Study A16 SAC cases; the overall reads (using both hemispheres) from each reader will be used for the second primary objective analysis.

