Like the analysis for primary objective 2, kappa statistics will be used to assess inter-reader reliability of flortaucipir F 18 PET scan visual interpretation with a τAD++ pattern. Fleiss' Kappa and the associated 95% CI will be calculated based on 5 readers' visual interpretations on the 242 scans (comprised of 83 scans from Study A16 autopsy cases, and 159 cases from Study A05). The p-value will be calculated using a normal approximation method. The lower bound of the 95% CI for Fleiss' Kappa must be greater than or equal to 0.6 to meet the inter-reader reliability criterion. If the scan is selected (by random) to be read twice for the intra-reader reliability assessment, the first read will be used for this analysis; for Study A16 SAC cases, the overall reads (using both hemispheres) from each reader will be used for this analysis.

5.4.2.3. Analysis for Secondary Objective 3

For this objective, inter-reader reliability of flortaucipir F 18 PET scan visual interpretation in the Study A05 scans, a population similar to the intended population for clinical use will be assessed similar to the second primary objective analysis except that the Fleiss' Kappa will be calculated based on 5 readers' visual interpretations on the 159 scans from Study A05. If any of the scans are selected (by random) to be read twice for the intra-reader reliability assessment, the first read will be used for this analysis. As an exploratory analysis, a similar analysis will be conducted using Study A16 scans.

5.4.2.4. Analysis for Secondary Objective 4

Twenty scans will be randomly selected for this analysis, and the 5 readers will read them in random sequence along with other scans. Cohen's Kappa will be calculated for each of these 5 readers, based on these 20 scans read repeatedly to assess the intra-reader reliability of flortaucipir F 18 PET scan visual interpretation. The 95% CI as well as p-values will be calculated using normal approximation method.

6. Study Documentation

Avid will be responsible for the submission of the protocol to the Instututional Review Board/Independent Ethics Committee for regulatory approval prior to start of the study.

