10.2. Multiple comparisons/multiplicity of hypotheses testing

Three hypotheses will be tested for the two co-primary objectives, as detailed in section 10.3. This trial will be considered successful if all three primary efficacy analyses achieve their success criteria.

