10.3. Analyses of the Primary Objectives

10.3.1. Primary Objective #1 Efficacy Analysis 1: Accuracy of Flortaucipir F 18 PET Scan Interpreted as AD Pattern in Detecting NFT Tau Stage

The first primary analysis will evaluate the accuracy of flortaucipir F 18 PET scan in detecting neurofibrillary tangle as measured by NFT stage (truth standard), as detailed in Table 1 of section 9.2. The hypothesis to be tested is that for at least the same 3 out of 5 independent readers, the lower bound of the two-sided 95% CI for both sensitivity and specificity of flortaucipir PET reading interpretations will be $\geq 50\%$.

This analysis will be based on the EFFA, as defined in 7.2.1.

The following table contains terms used to define sensitivity, specificity, accuracy, positive predictive value (PPV), negative predictive value (NPV), likelihood ratio positive (LR+) and likelihood ratio negative (LR-):

Diagnostic Test: Flortaucipir F 18 PET Scan Read Result	Truth Standard	
	NFT B3	NFT B0-B2
Positive: Flortaucipir F 18 neocortical uptake; AD pattern (τ AD+, τ AD++)	True Positive (TP)	False Positive (FP)
Negative: Flortaucipir F 18 neocortical uptake; not consistent with AD pattern (τ AD-)	False Negative (FN)	True Negative (TN)

The sensitivity, which evaluates how good a test is at detecting a positive disease, will be calculated as:

$$100 \times \frac{TP}{TP + FN}$$

The specificity, which estimates how likely subjects without the disease can be correctly ruled out, will be calculated as:

$$100 \times \frac{TN}{FP + TN}$$

The accuracy, which evaluates the overall proportion of observed agreement, will be calculated as:

$$100 \times \frac{TP + TN}{TP + FN + FP + TN}$$

The PPV, which is the proportion of positive test results that are true positives, will be calculated as:

$$100 \times \frac{TP}{TP + FP}$$

The NPV, which is the proportion of subjects with a negative test result who are correctly diagnosed, will be calculated as:

$$100 \times \frac{TN}{FN + TN}$$

The 95% CIs provided for specificity, sensitivity, accuracy, PPV and NPV will be based on the Wilson score method (Wilson 1927; Newcombe 1998).

The LR+, which is true positive rate divided by the false positive rate, will be calculated as:

$$\frac{\text{sensitivity}}{1 - \text{specificity}}$$

The LR-, which is the false negative rate divided by the true negative rate, will be calculated as:

$$\frac{1 - \text{sensitivity}}{\text{specificity}}$$

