10.3.2. Primary Objective #1 Efficacy Analysis #2: Accuracy of Flortaucipir F 18 PET Scan Interpreted as AD Pattern in Detecting AD Neuropathological Change

This analysis will evaluate the accuracy of flortaucipir F 18 PET scan in detecting High AD neuropathological change (ADNC), as detailed in Table 2 of section 9.2. Like primary analysis #1, the hypothesis to be tested is that for at least the same 3 out of 5 independent readers, the lower bound of the two-sided 95% CI for both sensitivity and specificity of flortaucipir PET reading interpretations will be $\geq 50\%$.

This analysis will be based on the EFFA, as defined in 7.2.1.

The calculation of sensitivity, specificity, NPV, PPV, LR+ and LR- analyses, as well as the confidence interval calculation will be identical to primary analysis #1, with ADNC as TS.

10.3.3. Primary Objective #2 Efficacy Analysis: Inter-Reader Agreement of Flortaucipir F 18 PET Scan Interpreted as AD Pattern

The overall reader to reader reliability across 5 readers for interpreting the flortaucipir PET scan will be assessed using Fleiss’ Kappa. The primary hypothesis to be tested is that the lower bound of two-sided 95% confidence interval of Fleiss’ Kappa will be greater than or equal to 0.6. This analysis will be based on the EFFP1, as defined in 7.2.2.1.

The degree of agreement between two readers for the interpretation of flortaucipir PET scan will be assessed in a pair-wise manner using Cohen’s Kappa statistics.

The percent of agreement between the two readers will be calculated for each reader pair. The over percent of agreement across 5 readers will be calculated too. All these results will be summarized in tables.

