10.4. Analysis of Secondary Objectives

10.4.1. Test the Relationship Between Ante-mortem Flortaucipir F 18 PET Imaging of an AD Pattern with Uptake Beyond the Temporal/Occipital Regions (τ AD++) and Tau Neurofibrillary Pathology Associated with AD, as Measured at Autopsy

To further evaluation the diagnostic performance of flortaucipir scans, the same scan interpretation from the readers will be reclassified as an AD pattern with uptake beyond the temporal/occipital regions (τ AD++: positive) vs. otherwise (τ AD+/ τ AD-: negative) and compared to the TS as detailed in section 9.2. That is, calculating the diagnostic performance statistics following the tables as below:

Secondary Objective #1 Efficacy Analysis #1

Diagnostic Test: Flortaucipir F 18 PET Scan Read Result	Truth Standard	
	NFT Score B3 [Truth Positive]	NFT Score B0–B2 [Truth Negative]
Positive: Flortaucipir F 18 neocortical uptake; τ AD++ pattern	True Positive (TP)	False Positive (FP)
Negative: Flortaucipir F 18 neocortical uptake; non- τ AD++ pattern (τ AD-/ τ AD+)	False Negative (FN)	True Negative (TN)

And:

Secondary Objective #1 Efficacy Analysis #2

Diagnostic Test: Flortaucipir F 18 PET Scan Read Result	Truth Standard	
	High AD Neuropathologic Change [Truth Positive]	Not, Low, or Intermediate AD Neuropathologic Change [Truth Negative]
Positive: Flortaucipir F 18 neocortical uptake; τ AD++ pattern	True Positive (TP)	False Positive (FP)
Negative: Flortaucipir F 18 neocortical uptake; non- τ AD++ pattern (τ AD-/ τ AD+)	False Negative (FN)	True Negative (TN)

The calculation of sensitivity, specificity, NPV, PPV, LR+, LR-, as well as the associate 95% CI will be the same as described in section 10.3.1.

10.4.2. Inter-Reader Reliability of Flortaucipir F 18 PET Scan Interpreted as τ AD++ Pattern

This analysis will assess the reliability of flortaucipir F 18 scan interpreted as τ AD++ pattern across 5 readers. Same as analysis described in section 10.3.3, Fleiss' Kappa and the associated two-sided 95% CI will be calculated. The hypothesis to be tested is that the lower bound of two-sided 95% confidence interval of Fleiss' Kappa will be greater than or equal to 0.6. This analysis will be based on the EFP1, as defined in 7.2.2.1.

10.4.3. Inter-Reader Agreement of Flortaucipir F 18 PET Scan Interpreted as AD Pattern for Intended Clinical Use Population

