The subjects enrolled in study A05 were representative cases of the intended clinical use population for flortaucipir F 18 scan. This analysis will evaluate the inter-reader reliability of flortaucipir scan interpreted as AD pattern with this intended clinical practice population. Analyses similar to 10.3.3 will be conducted using EFP2, which will be based on 159 A05 cases as defined in 7.2.2.2.

10.4.4. Intra-Reader Agreement of Flortaucipir F 18 PET Scan Visual Interpretation Interpreted as AD Pattern

Intra-reader reliability will be assessed using randomly selected 20 cases (EFP3) as defined in section 7.2.2.3. These randomly selected cases will be read twice by every reader. A Cohen's Kappa statistics will be used to assess the agreement of the two reading results (scans that are interpreted as an AD pattern, i.e., τ AD (τ AD+/ τ AD++) vs τ AD-) by every reader.

The percent of agreement between the two readings from same reader will be calculated for each reader. All these results will be summarized in tables.

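### Does leaving the standard error for the Fleiss' kappa confidence interval unnamed put the inter-reader co-primary result in doubt?

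*Protocol*

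**What the plan says.** Protocol 5.4.1.2 states that Fleiss' "Kappa and the associated 95% CI will be calculated based on 5 readers" and the 242 scans, and that the lower limit must reach 0.6. The next method it names is a normal approximation, and grammatically that belongs to the p-value.

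Protocol 5.1 passes the detail on: "The specific analyses to address the objectives will be described in the Statistical Analysis Plan". SAP 10.3.3 restates the criterion ("The primary hypothesis to be tested is that the lower bound of two-sided 95% confidence interval of" Fleiss' kappa is to be 0.6 or more) without giving a standard error, an interval formula or a SAS procedure. SAP 10.4.2 ("Kappa and the associated two-sided 95% CI will be calculated") and SAP 10.4.3 ("Analyses similar to 10.3.3 will be conducted using EFP2") both refer back to 10.3.3 and so inherit whatever is done there.

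Elsewhere the plan does name interval methods. For accuracy measures, SAP 10.3.1 says: "The 95% CIs provided for specificity, sensitivity, accuracy, PPV and NPV will be based on the Wilson score method". For the intra-reader Cohen's kappa, Protocol 5.4.2.4 says: "The 95% CI as well as p-values will be calculated using normal approximation method".

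The criterion carries full weight. SAP 10.2 states: "This trial will be considered successful if all three primary efficacy analyses achieve their success criteria".

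**The concern.** A secondary analysis of 20 scans has an explicit interval rule, while a co-primary criterion that can fail the trial on its own has none. Reading the normal approximation across from the p-value would fix only the form of the interval, estimate ± 1.96 × SE. It would not fix the SE.

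Two standard errors fit the words. One is derived under the hypothesis of no agreement beyond chance. It depends only on the numbers of scans and readers. The other is evaluated at the agreement actually observed and, for kappa near 0.65, is about one and a half times as large. Two analysts following the text could therefore reach opposite verdicts from the same reads. If the smaller SE were used, the criterion would be too easy to pass when true agreement sits exactly at 0.6.

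**Working it through.** **Inputs from the documents.** N = 242 scans and m = 5 readers; planning kappa 0.7 against 0.6, two-sided alpha 0.05, power over 90% (Protocol 5.3, SAP 5); majority-read positive rate about 56% (SAP 6). **Assumption.** The documents give no pattern of reader disagreement, so the simulations use several assumed rating models.

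**1. The plan's own power figure.** Power ≈ Φ(0.1/SE − 1.96).
- Power of 90% requires SE ≤ 0.1/(1.960 + 1.282) = 0.0308.
- SE under kappa = 0: √(2/(N·m·(m−1))) = √(2/(242·5·4)) = 0.0203, giving 99.8% (97–98% simulated).
- SE valid at kappa 0.7, 56% positive, beta-binomial or latent-class model: about 0.027–0.030, giving 91–95% (90–94% simulated).

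Both are consistent with over 90%, so the power statement does not show that the kappa = 0 formula was intended.

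**2. One table, several intervals.** Take 242 scans with 0, 1, 2, 3, 4, 5 positive reads in 68, 22, 16, 20, 28, 88 scans. Majority-positive scans: 20 + 28 + 88 = 136, or 56%.
- Pairwise agreement per scan is 1 for 0 or 5 positive reads, 0.6 for 1 or 4, and 0.4 for 2 or 3. Mean = (156 + 0.6·50 + 0.4·36)/242 = 200.4/242 = 0.8281.
- Proportion of positive reads = 666/1210 = 0.5504. Chance agreement = 0.5504² + 0.4496² = 0.5051.
- Kappa = (0.8281 − 0.5051)/(1 − 0.5051) = 0.653.

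| Method | SE | Lower 95% limit | At least 0.6? |
|---|---|---|---|
| kappa = 0 formula | 0.0203 | 0.613 | yes |
| Scan-level jackknife | 0.0312 | 0.592 | no |
| Delta method | 0.0311 | 0.592 | no |
| Percentile bootstrap | – | 0.589 | no |

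The three methods that allow kappa above zero agree to within 0.003. Only the kappa = 0 formula departs from them.

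**3. Where the verdict turns.** With the kappa = 0 SE, the smallest passing kappa is 0.6 + 1.96·0.0203 = 0.640. With the jackknife it is 0.656–0.666, depending on the rating model. Outside that window the verdicts agree.

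**4. How often.** Simulated at 56% positive, N = 242, five assumed models (beta-binomial, common-draw, all-or-none, latent-class, probit random effect), 10,000 datasets per setting:

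| True kappa | Verdicts differ |
|---|---|
| 0.60 | 6–9% |
| 0.65 | 22–29% |
| 0.70 (plan's value) | 5–12% |

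At true kappa 0.60 the criterion is passed 8.5–11.5% of the time with the kappa = 0 SE and 2.5–2.8% with the jackknife, against a nominal 2.5%. Coverage of the interval is 74–85% and 94.5–95.4% respectively.

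**The case for a change.** The best case for acting is that the omission is real, affects a co-primary criterion and could be closed with one sentence. The SAP's reference list includes a general textbook on rates and proportions, but no text on kappa cites it, so it settles nothing. A pass rate of 8.5–11.5% at the boundary, where 2.5% is intended, would be material. If analysts would choose the valid SE anyway, writing it down costs nothing.

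The facts in that argument stand. What does not follow is that the plan, as written, gives a wrong result. The inflated rate belongs to one specific choice: an SE that holds only when kappa is zero, used for an interval judged against 0.6. No section states or implies that choice. The plan asks for an interval around an estimate expected to be near 0.7, and an SE suited to that task is the ordinary reading. The options left to a careful analyst are jackknife, delta method and bootstrap, and they give practically the same limit. The argument about choosing after the reads are seen is also conditional, since nothing in the documents suggests it.

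The worked table was placed inside the window where verdicts differ, and the largest disagreement rates apply at a true kappa of 0.65, which is not a planning value. For the A05 scans alone, the 0.6 bound is inferred: the documents call for a similar analysis but do not restate the criterion.

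**Conclusion.** No change follows. The gap is one of written detail: the form of the interval is reasonably clear from the normal approximations named for the other kappa results, the SE is not named, and any SE valid at non-zero kappa leads to a sound conclusion. The departure would arise only if the kappa = 0 SE (0.0203) were used and the observed kappa fell between 0.640 and roughly 0.656–0.666. At the planned kappa of 0.70 that amounts to about 5–12% of studies.

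Those rates rest on a 56% positive rate and on rating models that the documents do not supply; the two-model check gives 5–8%. The τAD++ analysis could not be sized because no positive rate is given for it. A sponsor who wished to name the SE in SAP 10.3.3 could do so without cost, and SAP 10.4.2 and 10.4.3 would follow it, but the validity of the planned conclusion does not depend on it.

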5.4.2. Secondary Analyses

Four secondary objectives/analyses will further evaluate the precision of flortaucipir PET scan results.

5.4.2.1. Analyses for Secondary Objective 1

With the same TS as used in primary analyses 1 and 2, these secondary analyses will assess the diagnostic performance (sensitivity/specificity) of a $\tau AD++$ pattern found on flortaucipir PET scan interpretation as below:

Table 4. Secondary Objective 1 Analysis 1: Diagnostic Performance
Calculations for Flortaucipir F 18 PET Scan Reader Interpretation
vs. Autopsy NFT Score Truth Standard

	Autopsy NFT Score TS	
Physician Reader Interpretation	NFT Score B3	NFT Score B0–B2
1 nystetun reduct interpretation	[Truth Positive]	[Truth Negative]
Flortaucipir F 18 neocortical uptake; τAD++ pattern	True Positive (TP)	False Positive (FP)
Flortaucipir F 18 neocortical uptake; non- τAD++ pattern (τAD- or τAD+)	False Negative (FN)	True Negative (TN)

Table 5. Secondary Objective 1 Analysis 2: Diagnostic Performance
Calculations for Flortaucipir F 18 PET Scan Reader Interpretation
vs. NIA-AA Autopsy Diagnosis Truth Standard

	NIA-AA Autopsy Diagnosis TS		
Physician Reader Interpretation	High AD Neuropathologic Change	Not, Low, or Intermediate AD Neuropathologic Change	
	[Truth Positive]	[Truth Negative]	
Flortaucipir F 18 neocortical uptake; τAD++ pattern	True Positive (TP)	False Positive (FP)	
Flortaucipir F 18 neocortical uptake; non-τAD++ pattern (τAD- or τAD+)	False Negative (FN)	True Negative (TN)	

Two-sided 95% CIs will be calculated using the Wilson score method. The second primary endpoint is met if for the same 3 out of 5 readers, the lower bounds of the 95% CIs for both sensitivity and specificity are \geq 50%.

The pathological diagnosis (for both NFT score TS and NIA-AA autopsy diagnosis TS) for Study A16 SAC cases were based on tissue samplings from 1 side of the brain. Therefore, the

reads from the corresponding hemisphere upon which the pathological diagnosis was based on will be used for secondary objective 1, analyses 1 and 2.

For both analyses as listed above, the hypotheses for testing are that for the same 3 out of 5 readers, the lower bound of the 95% CIs for both sensitivity and the specificity will be \geq 50%.

5.4.2.2. Analysis for Secondary Objective 2

Like the analysis for primary objective 2, kappa statistics will be used to assess inter-reader reliability of flortaucipir F 18 PET scan visual interpretation with a τAD++ pattern. Fleiss' Kappa and the associated 95% CI will be calculated based on 5 readers' visual interpretations on the 242 scans (comprised of 83 scans from Study A16 autopsy cases, and 159 cases from Study A05). The p-value will be calculated using a normal approximation method. The lower bound of the 95% CI for Fleiss' Kappa must be greater than or equal to 0.6 to meet the inter-reader reliability criterion. If the scan is selected (by random) to be read twice for the intra-reader reliability assessment, the first read will be used for this analysis; for Study A16 SAC cases, the overall reads (using both hemispheres) from each reader will be used for this analysis.

5.4.2.3. Analysis for Secondary Objective 3

For this objective, inter-reader reliability of flortaucipir F 18 PET scan visual interpretation in the Study A05 scans, a population similar to the intended population for clinical use will be assessed similar to the second primary objective analysis except that the Fleiss' Kappa will be calculated based on 5 readers' visual interpretations on the 159 scans from Study A05. If any of the scans are selected (by random) to be read twice for the intra-reader reliability assessment, the first read will be used for this analysis. As an exploratory analysis, a similar analysis will be conducted using Study A16 scans.

5.4.2.4. Analysis for Secondary Objective 4

Twenty scans will be randomly selected for this analysis, and the 5 readers will read them in random sequence along with other scans. Cohen's Kappa will be calculated for each of these 5 readers, based on these 20 scans read repeatedly to assess the intra-reader reliability of flortaucipir F 18 PET scan visual interpretation. The 95% CI as well as p-values will be calculated using normal approximation method.

6. Study Documentation

Avid will be responsible for the submission of the protocol to the Instututional Review Board/Independent Ethics Committee for regulatory approval prior to start of the study.

All data required by the protocol will be recorded in the eCRF. Completed eCRFs may need to be made available for an audit by the United States Food and Drug Administration or other international regulatory authorities at any time. The eCRFs and all other records will be filed in accordance with applicable laws and regulations.

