2.2. Secondary Objectives

- Test the relationship between ante-mortem flortaucipir F 18 PET imaging of an AD pattern with uptake beyond the temporal/occipital regions (i.e., τAD++; see Table 1) and tau neurofibrillary pathology associated with AD, as measured at autopsy.
- Assess inter-reader reliability for scans with an AD pattern that is beyond the temporal/occipital regions (i.e., $\tau AD++$; see Table 1).
- Assess agreement among readers of flortaucipir F 18 PET scans in subjects known to be from the intended population (interpretation of scans from Avid Study ¹⁸F-AV-1451-A05 [A05]).
- Assess intra-reader reliability for scans read twice by each reader.

3. Study Design

All training and reads will be conducted by an imaging contract research organization (CRO) as described in the imaging review charter (IRC). Five readers will be trained in-person on the flortaucipir F 18 PET scan read methodology using the previously developed read method. The training will consist of teaching the readers the steps of interpretation, followed by a practice session using a set of demonstration and practice cases. After the training phase is complete, readers will then independently read 262 scans; 83 from Study ¹⁸F-AV-1451-A16 (A16) and 159 from Study A05.

The study population for Study A16 (¹⁸F-AV-1451-A16: A clinico-pathological study of the correspondence between ¹⁸F-AV-1451 PET imaging and post-mortem assessment of tau pathology) consisted of subjects at the end of life, who were imaged with flortaucipir F 18 and came to autopsy. Subjects were enrolled in the study with the intent of capturing a range of tau neurofibrillary pathology in AD.

The study population for Study A05 confirmatory cohort (¹⁸F-AV-1451-A05: An open label, multicenter study, evaluating the safety and imaging characteristics of ¹⁸F-AV-1451 in cognitively healthy volunteers, subjects with mild cognitive impairment, and subjects with Alzheimer's disease) consisted of subjects with cognitive impairment who had mild cognitive impairment (MCI) or dementia with a suspected neurodegenerative cause, and a Mini Mental State Examination (MMSE) score of 20-27, inclusive. Subjects were imaged with flortaucipir F 18 and followed longitudinally for 18 months to assess the subsequent rate of cognitive decline.

4. Procedures and Methods

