4.2. Selection/Number of Images

Two hundred and forty-two unique scans will be read for this study, comprised of the following:

- All 83 subjects from Study A16 (primary and supplemental) who have a valid scan and autopsy
- All 159 subjects from the Study A05 confirmatory cohort who have a valid scan
- In addition, a sub-set of 20 randomly selected cases will be used for intra-reader reliability purposes for a total of 262 scan reads

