5.2.2. Analysis Population for Scan Interpretation Precision Assessment

The precision of flortaucipir F 18 PET scan interpretation will be assessed in 2 ways: interreader (i.e., reader-to-reader) reliability, and intra-reader reliability (i.e., agreement between the repeated reads on same scan from same reader). The inter-reader reliability will be assessed using all 242 scans included for this study (83 Study A16 scans and 159 Study A05 scans). The inter-reader reliability will also be assessed separately on the 159 Study A05 scans (i.e., the targeted population for clinical usage), and on the 83 Study A16 scans. Twenty scans will be randomly selected and will be read twice by the 5 readers in a randomized sequence, along with all the other scans. The repeated reads on these 20 scans will be used to assess the intra-reader reliability.

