6. FLORTAUCIPIR PET SCAN SELECTION

Flortaucipir F 18 PET scans were selected from subjects enrolled in previous studies ^{18}F -AV-1451-A16 and ^{18}F -AV-1451-A05. The following images will be used for this study:

- All 83 subjects from Study A16 (primary and supplemental) who have a valid scan and autopsy. This includes:
 - 3 front-runners
 - 64 main study autopsy cases
 - 16 autopsy cases collected under SAC
- All 159 subjects from the study ^{18}F -AV-1451-A05 who have a valid scan, representing the intended population for clinical use.
- 20 scans will be randomly selected (by simple random selection method) from studies A16 and A05, to be read twice independently by each of the 5 readers for intra-reader reading reliability evaluation purposes.

The majority read results from A05 and A16 both showed a ~56% scan positive ($\tau\text{AD}^+/\tau\text{AD}^{++}$) rate. Similarly, it is expected that the 20 scans randomly selected for intra-reader reliability evaluation will have a similar scan positive rate. If by chance the randomly selected 20 cases have a skewed positive or negative rate, to avoid possible interpretation bias from a sample population of primarily positive or negative scans, the random sampling process will be repeated to ensure a relatively balanced positive/negative rate from the selected samples (scan positive rate by majority reads from corresponding study is in the range of 30% - 70%).

An external CRO will randomize all scans into a randomized sequence for visual reading.

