7.2.2.1. EFP1

EFP1 will include reading results for all valid and interpretable scans from all 242 cases from studies A16 and A05. The analysis set will be used to conduct primary objective #2 efficacy analysis (refer to Section 10.3.3), and secondary objective #2 efficacy analysis (refer to section 10.4.2).

For scans that will be read twice for intra-reader reliability evaluation, the first read will be included in the EFP1. For the 16 SAC cases, the overall visual interpretation based on whole brain will be used.

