10.5. Other Efficacy Analyses

10.5.1. Accuracy of Flortaucipir F 18 Scan in Detecting Tau Neurofibrillary Pathology Associated with Alzheimer's Disease (AD), Based on Majority Scan Interpretations

For each image, the majority interpretation of 5 independent readers will be derived using individual readers' interpretation results. Diagnostic performance of this majority interpretation will be assessed relative to the autopsy NFT score TS as per primary objective #1 efficacy analysis #1 (refer to Section **Error! Reference source not found.**0.3.1) and again relative to the NIA-AA autopsy diagnosis TS as per primary objective #1 efficacy analysis #2 (refer to Section **Error! Reference source not found.**0.3.2).

The sensitivity and specificity along with their two-sided 95% CIs (based on the Wilson score method) will be calculated for the majority interpretation of 5 independent readers relative to the appropriate TS.

The accuracy, PPV, NPV, LR+ and LR- of the flortaucipir F 18 PET imaging classification for the majority interpretation of 5 independent readers relative to the appropriate TS will be also calculated. Two-sided 95% CIs (based on the Wilson score method) will be provided for the accuracy, the PPV and NPV.

10.5.2. Inter-Reader Agreement of Flortaucipir F 18 PET Scan Interpreted as AD Pattern for Autopsy Population

The inter-reader agreement analysis across 5 readers of flortaucipir F 18 PET scan interpretation (interpreted as AD pattern) will be repeated based on the EFFA. Fleiss' Kappa, and other statistics, will be calculated the same as described in section 10.3.3.

10.5.3. Additional Visual Interpretation Reliability Assessment of Flortaucipir F 18 Scan Interpreted as τ AD++ Pattern

These additional visual interpretation reliability assessments will be conducted for flortaucipir F 18 scans based on the τ AD++ pattern:

1) Inter-reader reliability for scans including clinical use population only (A05 cases):

Fleiss' Kappa, and other statistics will be calculated the same as described in section 10.3.3., based on EFFP2.

2) Inter-reader reliability for scans including autopsy cases only (A16 cases):

Fleiss' Kappa, and other statistics will be calculated the same as described in section 10.3.3., based on EFFA.

3) Intra-reader reliability for scans included in EFP3:

Cohen’s kappa and other statistics will be calculated the same as described in section 10.4.4, based on EFP3.

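### Does the lack of a stated minimum gap between the two reads of each repeat scan undermine the intra-reader kappa?

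*Protocol*

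**What the plan says.** Protocol 4.2 fixes the workload: 242 unique scans, plus "a sub-set of 20 randomly selected cases will be used for intra-reader reliability purposes for a total of 262 scan reads". On ordering, Protocol 5.2.2 says the 20 scans "will be read twice by the 5 readers in a randomized sequence, along with all the other scans", and Protocol 5.4.2.4 repeats this: "Twenty scans will be randomly selected for this analysis, and the 5 readers will read them in random sequence along with other scans". SAP section 6 adds that the scans are "to be read twice independently by each of the 5 readers for intra-reader reading reliability evaluation purposes" and that "An external CRO will randomize all scans into a randomized sequence for visual reading".

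No minimum number of intervening reads, session split or washout appears in either document. Nor is it stated whether the five readers share one sequence. Both documents do, however, assign read conduct elsewhere: "All training and reads will be conducted by an imaging contract research organization (CRO) as described in the imaging review charter (IRC") (Protocol section 3, repeated in SAP section 4).

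The second reads feed two results only. One is the per-reader Cohen's kappa for secondary objective 4 (Protocol 5.4.2.4, SAP 10.4.4). The other is the τAD++ counterpart among the other efficacy analyses in SAP 10.5.3, item 3: "Intra-reader reliability for scans included in EFP3".

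**The concern.** Intra-reader reliability is meant to show that a reader, facing the same image afresh, reaches the same call. If the second copy appears a few reads after the first, the reader may recognise it and repeat the earlier answer. Agreement then partly reflects memory, and the expected shift favours the product.

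Purely random order does not prevent this. Blinding to clinical data (Protocol 4.3), withholding the protocol from readers (6.1) and anonymising scans (6.2) remove labels, but they do not hide a distinctive image. The SAP asks for independent second reads without stating how spacing would secure independence. With only 20 pairs per reader, a modest inflation could not be seen in the data. At stake would be the credibility of a named secondary objective that is reported with confidence intervals and p-values.

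**Working it through.** **Inputs.** Sequence length 83 + 159 + 20 = 262 reads per reader, which reproduces the total in Protocol 4.2. There are 20 repeat pairs per reader. The scan-positive rate is about 56% (SAP section 6). The documents give no recall length and no expected intra-reader kappa, so windows of 5 to 50 positions and true kappas of 0.7 to 0.9 are assumptions.

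**Step 1: how often repeats fall close together.** For two copies placed at random among L = 262 positions, the chance that their positions differ by at most g is

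P(gap ≤ g) = 2 × [gL − g(g+1)/2] / [L(L−1)], with L(L−1) = 262 × 261 = 68,382.

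| g | Numerator | P(gap ≤ g) | Expected pairs of 20 |
|---|---|---|---|
| 5 | 2 × (1,310 − 15) = 2,590 | 0.0379 | 0.76 |
| 10 | 2 × (2,620 − 55) = 5,130 | 0.0750 | 1.50 |
| 20 | 2 × (5,240 − 210) = 10,060 | 0.1471 | 2.94 |
| 50 | 2 × (13,100 − 1,275) = 23,650 | 0.3459 | 6.92 |

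The mean gap is (262 + 1)/3 ≈ 88 positions. Simulating 20 pairs in random order gives a 54% chance that a sequence holds at least one pair within 5 positions, and 79% within 10. A close repeat somewhere is therefore more likely than not if the order is unconstrained.

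**Step 2: what that does to kappa.** Suppose every pair inside the window is remembered perfectly. With a share f of pairs forced to agree, expected kappa moves from κ to about κ + f(1 − κ), a rise of f(1 − κ). For κ = 0.7 and g = 10 this is 0.0750 × 0.3 = 0.0225. Simulated rises with 20 pairs and 56% positive agree with the formula to within 0.003:

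| True κ | g = 5 | g = 10 | g = 20 | g = 50 |
|---|---|---|---|---|
| 0.7 | 0.012 | 0.023 | 0.045 | 0.107 |
| 0.8 | 0.008 | 0.015 | 0.030 | 0.071 |
| 0.9 | 0.004 | 0.008 | 0.015 | 0.037 |

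**Step 3: compare with sampling error.** Chance agreement is 0.56² + 0.44² = 0.5072. At κ = 0.7, observed agreement is 0.5072 + 0.7 × 0.4928 = 0.852, so the approximate SE is √(0.852 × 0.148 / 20) / 0.4928 = 0.16. The same formula gives 0.14 at 0.8 and 0.10 at 0.9; simulated SDs are 0.166, 0.141 and 0.104. At κ = 0.7 the 5-read rise is about 7% of the SD (0.012/0.166) and the 10-read rise about 14% (0.023/0.166).

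**Step 4: chance that any result changes.** Recall matters only for a pair that would otherwise disagree. At κ = 0.7 the disagreement rate is 0.148, so the chance that at least one of a reader's 20 pairs is altered is 1 − (1 − 0.0379 × 0.148)^20 ≈ 0.11 for 5 reads and about 0.20 for 10. At κ = 0.8 these are about 0.07 and 0.14.

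**Step 5: where second reads go.** For the overall inter-reader analysis, SAP 7.2.2.1 states: "For scans that will be read twice for intra-reader reliability evaluation, the first read will be included in the EFP1". SAP 7.2.1 and 7.2.2.2 say the same for the accuracy set and the A05 set, as does Protocol 5.4.1.2 for the inter-reader primary analysis. SAP 10.2 defines success by the three primary analyses. None of them contains a second read.

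**The case for a change.** The best argument for acting is that the sponsor already accepts a constraint on these same 20 scans. SAP section 6 redraws the sample if its positive rate falls outside 30% to 70%, in order to avoid interpretation bias. A spacing rule would be a similar constraint, would need no extra reads, and would directly serve the independence that the SAP asks for. The expected effect of recall is also in one direction, unlike sampling error.

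Much of this stands. The documents print no gap, close pairs are likely in an unconstrained list, and a gap would be cheap to impose. Three things limit it.

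- The absence of a rule from the protocol and SAP does not show its absence from the plan. Both documents name the charter as the place where read conduct is described, and ordering belongs there.
- The direction is probable, not certain: a reader who recognises a scan may also reconsider the call.
- The remedies carry their own costs. The documents support no particular gap. Requiring, for example, at least 50 intervening reads would raise the mean gap from 88 to about 50 + 213/3 = 121 positions, so more reader drift would count as disagreement. Excluding close pairs afterwards at a 50-read cut-off would drop about 7 of 20 pairs. The simulated SD with 13 pairs rises from 0.166 to 0.21 at κ = 0.7 and from 0.141 to 0.18 at κ = 0.8. That loss of about 0.04 exceeds the 5- and 10-read biases it would remove.

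**Conclusion.** No change is needed. The gap in the text is an operational detail that the charter or the CRO preparing the reading list can settle, and the plan as written still gives a sound result. With recall over 5 to 10 reads, the expected inflation of a reader's kappa is at most about 0.004 to 0.023, against a sampling SD of 0.10 to 0.17. It reaches about 0.07 to 0.11 (true kappa 0.8 to 0.7) only if readers remember every scan across 50 intervening positions, which is hard to credit with interleaved, anonymised images.

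The affected results are a secondary objective with no success threshold and one additional τAD++ analysis. Accuracy, inter-reader agreement and the trial-success rule are untouched.

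This conclusion rests on an unconstrained order (the worst case, since the charter may restrict it), perfect recall inside the window (an upper bound), a 56% positive rate, and true intra-reader kappa between 0.7 and 0.9.
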